10.2 General Statistical Methods

A detailed statistical analysis plan will be developed for each trial (acute pain, chronic pain, and

depression) and contained in a separate document. Prior to analysis, each trial study population details, including the number randomized, in each treatment arm, and lost to follow-up will be described. Baseline participant characteristics will be summarized as means, standard deviations, medians, and 25th, 75th percentiles for continuous variables, and as counts and percentages for categorical variables. Model assumptions will be examined prior to analysis and transformations implemented, if necessary, to more adequately meet the assumptions. Unless otherwise stated, hypotheses will be tested as two-sided with a significance level of 0.05.

10.3 Population for Analyses

Acute pain

Participants randomized who have an actionable phenotype, specifically participants who are genotypically or pheno-converted CYP2D6 IM or PMs (i.e. CYP2D6 activity score ≤ 0.75).

Chronic pain

Participants randomized who have an actionable phenotype, specifically participants who are genotypically or pheno-converted CYP2D6 IM or PMs (i.e. CYP2D6 activity score ≤ 0.75).

Depression

Participants randomized who have an actionable phenotype, specifically participants who are genotypically or pheno-converted CYP2D6 PM or UMs or CYP2C19 PM, RM, or UMs.

10.4 Analysis of the Primary Endpoint

Acute Pain

To determine the effect of genotype-guided drug therapy on pain control in acute pain participants, we will conduct a subset analysis comparing SIA scores at 10-days post-surgery in the Intervention group subset with CYP2D6 IM or PM phenotypes to the Control group subset with CYP2D6 IM or PM phenotypes. Participants that have other CYP2D6 phenotypes will not be included. The 10-day post-surgery SIA scores of the Intervention CYP2D6 IM/PM group will be compared to the 10-day post-surgery SIA scores of the Control CYP2D6 IM/PM group using a two-sided two-sample t-test or Mann Whitney test, as appropriate, with a type 1 error of 0.049. This primary analysis will be conducted as a modified intent-to-treat analysis, with participants analyzed and endpoints attributed according to the treatment arm to which the participants were randomized, regardless of subsequent crossover or post-randomization medical care.

Chronic Pain

To determine the effect of genotype-guided drug therapy on pain control in chronic pain participants, we will conduct a subset analysis comparing change in pain intensity score from baseline to 3-month follow-up in the Intervention group subset with CYP2D6 IM or PM phenotypes to the Control group subset with CYP2D6 IM or PM phenotypes. Participants that have other CYP2D6 phenotypes will not be included. The baseline to 3-month change in pain intensity of the Intervention CYP2D6 IM/PM group will be compared to the baseline to 3-month change in pain intensity of the Control CYP2D6 IM/PM group using a two-sided two-sample t-test or Mann Whitney test, as appropriate, with a type 1 error of 0.049. This primary analysis will be conducted according to modified intent-to-treat design, with participants analyzed and endpoints attributed according to the treatment arm to which the participants were randomized, regardless of subsequent crossover or post-randomization medical care.

Depression

To determine the effect of genotype-guided drug therapy on depression symptoms in depression

participants, we will conduct a subset analysis comparing change in depression T-scores from baseline to 3-month follow-up in the Intervention group subset with either CYP2D6 PM or UM or CYP2C19 PM, RM or UM phenotypes to the Control group subset with CYP2D6 PM or UM or CYP2C19 PM, RM, or UM phenotypes. Participants that have other CYP2D6 or CYP2C19 phenotypes will not be included. Pediatric depression T-scores will be transformed to the adult scale using a published crosswalk for a combined analysis. The baseline to 3-month change in depression T-scores of the Intervention CYP2D6 PM/UM or CYP2C19 PM/RM/UM group will be compared to the baseline to 3-month change in depression T-scores of the Control CYP2D6 PM/UM or CYP2C19 PM/RM/UM subgroup using a two-sided two-sample t-test with a type 1 error of 0.049. This primary analysis will be conducted according to a modified intent-to-treat design, with participants analyzed and endpoints attributed according to the treatment arm to which the participants were randomized, regardless of subsequent crossover or post-randomization medical care.

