- Overall well-being of all Intervention participants will be compared to the overall well-being of all Control participants at 6-month follow-up using ANOVA, adjusting for baseline differences in the two groups
- The effect of genotype guided therapy on concordance between phenotype and prescribed medication will be compared between Intervention and Control participants from the metabolizer phenotypic subgroups specified

	
for each trial's primary endpoint.
 
● Additional analyses will include time trends, subset analyses, and covariate adjustments analyses
--	---

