4.1 Randomization

After participants provide informed consent/assent, participants will be randomized in a 1:1 allocation to the Intervention (i.e. immediate PGx testing and genotype-guided opioid or SSRI therapy with clinical decision support) and Control (i.e. usual care with delayed PGx testing) arms. Randomization will be stratified by trial and site or clinic with a random block size within each site or clinic. We anticipate variability in patient populations between recruiting sites or clinics and aim to balance the intervention assignments within the site or clinic unit. Additionally, the randomization for the chronic pain trial will be stratified by presence/absence of depression, and the randomization for the acute pain and depression trials will be stratified by pediatric/adult.

The randomization scheme will be generated by an unblinded statistician. Randomization assignments will be generated in real time in REDCap at the Coordinating Center.

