Medication side effects. The frequency and severity of medication side effects within each trial and trial arm will be summarized using standard descriptive statistics for discrete data (counts and percentages).

Acute Pain

Trends in endpoints. In addition to the primary and secondary endpoints described above, we will compare the time trends in the endpoints: pain scores, opioid usage, opioid misuse score, and mobility score at baseline, 1, 3, and 6 months among the CYP2D6 IM or PM subgroup, using a repeated-measures mixed effect model or generalized repeated-measures mixed effect model, as appropriate. Since participants are randomized to Intervention and Control groups and not to the CYP2D6 IM or PM subgroup within Intervention and Control groups, there could be important differences in baseline characteristics between the two groups. For these reasons, we will conduct covariate-adjusted repeated measures mixed models that will account for differences in baseline characteristics that differ between the Intervention – CYP2D6 IM or PM subgroup and the Control – CYP2D6 IM or PM subgroup. Potential baseline characteristics may include age, sex, income, education, insurance, surgical procedure type. We will select the appropriate covariance matrix (e.g. compound symmetry, autoregressive, unstructured, or other covariance structure) based on the data.

Difference within the NM group. In the control arm participants, we will compare pain scores in participants with a CYP2D6 activity score $>0.75 - 1$ to participants with an activity scores $>1-2$ using a two-sided two-sample t-test or Mann Whitney test, as appropriate, with a type 1 error of 0.05. Additionally, we will use linear regression to adjust for differences in baseline characteristics.

Chronic Pain

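### All three primary tests are unadjusted for baseline and randomisation strata; a prespecified ANCOVA would gain power in chronic pain and depression at no extra sample size

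*Combined protocol and SAP*

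**What the plan says.** Section 10.4 names the primary test for each trial, in the actionable-phenotype subset, at two-sided 0.049:

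- Acute pain: the intervention arm is compared with the "10-day post-surgery SIA scores of the Control CYP2D6 IM/PM group using a two-sided two-sample t-test or Mann Whitney test, as appropriate".
- Chronic pain: the intervention arm's change is compared with the "baseline to 3-month change in pain intensity of the Control CYP2D6 IM/PM group using a two-sided two-sample t-test or Mann Whitney test, as appropriate".
- Depression: the intervention arm's change is "compared to the baseline to 3-month change in depression T-scores of the Control CYP2D6 PM/UM or CYP2C19 PM/RM/UM subgroup using a two-sided two-sample t-test".

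No covariate enters any of them. Section 4.1 says "Randomization will be stratified by trial and site or clinic with a random block size within each site or clinic", and adds a second factor: "the randomization for the chronic pain trial will be stratified by presence/absence of depression", and pediatric/adult status in the other two trials.

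Section 10.6 notes that participants were not randomised within the phenotype subset, so that "there could be important differences in baseline characteristics between the two groups". Its response is confined to exploratory mixed models, which "account for differences in baseline characteristics that differ between the Intervention" and control subgroups. The synopsis also lists covariate adjustment among the additional analyses. For well-being, a secondary endpoint, the synopsis plans a comparison "at 6-month follow-up using ANOVA, adjusting for baseline differences in the two groups", although Section 10.5 gives the same endpoint an unadjusted test.

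**The concern.** A change score fixes the coefficient of the baseline value at 1. Unless baseline and follow-up are almost perfectly correlated, that over-corrects: it adds baseline noise and leaves the estimate exposed to chance baseline differences through regression to the mean. Analysing follow-up alone, as in acute pain, fixes the coefficient at 0 and discards whatever baseline pain predicts. ANCOVA estimates the coefficient.

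The analysed sets are modest (304, 268 and 542), and the plan itself expects that the arms may differ at baseline within them. It nevertheless adjusts only in exploratory models, for covariates picked because they turn out to differ, which makes the model depend on the data. Factors important enough to stratify by are left out of the primary test.

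**Working it through.** **Inputs from the documents.** Section 10.1 and Table 9: two-sided alpha 0.049; 90% power; standardised effects and numbers per arm of 0.375 and 152 (acute), 0.40 and 134 (chronic), 0.28 and 271 (depression). Synopsis: 11 sites, about 60-80 clinics. Section 7.3: pain is surveyed at baseline in acute pain, but opioid consumption only at 10 days and 1 month, so no baseline SIA exists.

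**Assumptions.** The correlation rho between baseline and follow-up is not given; I use 0.3, 0.5 and 0.7. For baseline pain with the 10-day SIA score I use r from 0 to 0.5. Variances are taken as equal at baseline and follow-up.

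**1. The plan's own figures.** Noncentral-t solutions for 90% power are 151.2, 133.02 and 270.4 per arm, which round up to the stated 152, 134 and 271. Power at those sizes is 90.1%, 90.2% and 90.1%.

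**2. Baseline ANCOVA against the change score.** With score variance s², Var(change) = 2s²(1 − rho) and Var(ANCOVA residual) = s²(1 − rho²). The ratio is (1 + rho)/2, that is 0.65, 0.75 and 0.85. Taking the planned effects as being on the change scale, and dividing each by the square root of the ratio:

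| | unadjusted | rho 0.3 | rho 0.5 | rho 0.7 |
|---|---|---|---|---|
| Chronic pain, 134 per arm | 90.2% | 98.1% | 96.4% | 94.2% |
| Depression, 271 per arm | 90.1% | 98.1% | 96.3% | 94.1% |

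**3. Cost of stratum terms.** I added K stratum terms and one binary factor, all assumed to explain nothing, averaged over 400 simulated designs with arm independent of stratum.

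| | rho 0.3 | rho 0.5 | rho 0.7 |
|---|---|---|---|
| Chronic pain, K = 11 | 97.6% | 95.7% | 93.2% |
| Depression, K = 11 | 97.8% | 96.0% | 93.6% |
| Chronic pain, K = 80 | 92% | 88% | 84% |
| Depression, K = 80 | 96% | 93% | 90% |

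Site terms are cheap. Clinic terms in chronic pain can cost more than baseline adjustment gains. Stratified randomisation balances arms better than these designs do, so the costs are probably overstated.

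**4. Acute pain.** The variance ratio against the 10-day score alone is 1 − r². With baseline pain only, 90.1% becomes 90.4%, 92.6% and 96.4% at r = 0.1, 0.3 and 0.5. With 11 uninformative site terms and the binary factor it is 88.9%, 89.2%, about 91.5% and 95.7% at r = 0, 0.1, 0.3 and 0.5. Break-even is at r of about 0.2.

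**5. Chance baseline differences.** The 95% limit is 1.96 × √(2/n): 0.24 SD with 134 per arm and 0.17 SD with 271. The change-score estimate moves by (1 − rho) times this. At rho 0.5, where the SDs of change and score coincide, that is 0.12 and 0.08 SD, about 30% of the planned 0.40 and 0.28. ANCOVA removes the shift.

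**6. Ignored strata.** In a simulation of chronic pain (4,000 runs, 20 balanced strata, rho 0.5), with strata assumed to explain 10% of the variance, the t-test rejected 3.5% of the time under the null against a nominal 4.9%. A model with baseline and strata rejected 4.4%. Leaving the strata out is therefore conservative; it does not inflate type I error.

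**7. The depression SD.** Section 10.1 gives an SD of 10 without saying whether it is of the score or of the change. If it is of the score, the SD of change is 10 × √(2(1 − rho)), and the change-score test has 78% or 84% power at rho 0.3 or 0.4, against 92.5% or 94.3% for ANCOVA. The two readings coincide at rho 0.5.

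**The case against.** The unadjusted tests are valid and the trials were sized for them, so nothing is broken. Chance imbalance is already inside the t-test's standard error; the shifts in step 5 are 95% extremes, and they are another view of the variance in step 2, not an additional loss. All of that stands, and it is why this is a suggestion for improvement.

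The size of the gain rests on an undocumented correlation. The one clue is in Section 10.1, where chronic pain shows the same standardised effect for the score and for its 3-month change. If the raw difference was also the same, rho is near 0.5 and the figure to expect is about 96%, not 98%. The direction does not depend on this: baseline ANCOVA beats a change score at any rho below 1.

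For acute pain the objection is stronger. Baseline pain is only a proxy for a rank composite of pain and opioid use, and the full model could lose about 1 point of power. Also, where clinic was the stratum, a model with site still omits it.

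Section 10.2 defers detail to separate SAPs, which are not available here, and Section 10.8 plans multiple imputation, whose model may use baseline data. Neither changes the primary test that Section 10.4 names. Finally, the synopsis describes the depression test as comparing 3-month scores, in conflict with 10.4. On that reading the ratio is 1 − rho² and ANCOVA power would be 92.5%, 96.3% and 99.5% at rho 0.3, 0.5 and 0.7. This favours ANCOVA, whose treatment estimate is the same whether the outcome is the score or the change.

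**Conclusion.** The concern holds as a matter worth considering. The description of the plan is certain; the size of the benefit is conditional. For chronic pain and depression, baseline plus site adjustment raises power from 90% to roughly 93-98% over an assumed rho of 0.3 to 0.7, given equal variances and planned effects on the change scale. It also removes sensitivity to chance baseline differences that could move the estimate by up to about 30% of the planned effect at rho 0.5. If the depression SD of 10 is cross-sectional and rho is below 0.5, the named test falls short of 90% while ANCOVA does not. For acute pain the result ranges from a loss of about 1 point to a gain of about 6, depending on how well baseline pain predicts the SIA score. ANCOVA does not address bias from open-label reporting or from differential dropout.

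**What to change.** - **Section 10.4:** make the primary test a linear model at two-sided 0.049 with arm, the baseline value of the endpoint, site, and the second stratification factor (depression yes/no in chronic pain; pediatric/adult in the other two). For acute pain use a baseline pain score; Table 8 marks the numeric rating scale as the primary-endpoint pain measure. Use site, not clinic, and pool sites below a stated size. Keep the unadjusted t-test or Mann-Whitney as a sensitivity analysis. This also removes the open choice between those two tests in the pain trials.
- **Section 10.7:** base the interim test and conditional power on the same model.
- **Section 10.6:** list the covariates in advance instead of selecting those that differ between arms.
- **Section 10.1:** state whether the depression SD of 10 is of the score or of the change.
- **Synopsis:** align the depression test with 10.4, and the well-being analysis with 10.5.

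The cost is wording and a pooling rule; no new data or participants are needed. The documents do not say whether the interim analysis has taken place, so the change should be dated and made before any comparison of outcomes by arm.

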10.5 Analysis of the Secondary Endpoints

All Trials

To determine the effect of genotype-guided drug therapy on overall well-being and the well-being sub-domains (pain interference, physical function, sleep disturbance, social role and activities functioning, fatigue, anxiety, and depression) in acute pain, chronic pain, and depression participants, we will conduct an intent to treat analysis, comparing the well-being (or sub-domain) T-scores from the 6-month follow-up assessments in the Intervention group compared to the control group using a two-sided two-sample t-test or Mann Whitney test, as appropriate, stratified by participant population (acute pain, chronic pain, depression), with a type 1 error of 0.05.

Acute Pain

The effect of genotype-guided opioid therapy on secondary endpoints pain intensity, opioid usage, opioid misuse score, and mobility score will be assessed by comparing the Intervention group subset with CYP2D6 IM or PM phenotypes to the Control group subset with CYP2D6 IM or PM phenotypes using a two-sided two-sample t-test or Mann Whitney test, as appropriate, with a type 1 error of 0.05. The effect of genotype guided opioid therapy on the secondary endpoint opioid persistence will be assessed by comparing the Intervention group subset with CYP2D6 IM or PM phenotypes the Control group subset with CYP2D6 IM or PM phenotypes using a test of two-proportions with an alpha of 0.05. Participants with other CYP2D6 phenotypes will not be included in these analyses.

Chronic Pain

The effect of genotype-guided opioid therapy on secondary endpoints pain intensity reduction and opioid misuse score will be assessed by comparing the Intervention group subset with CYP2D6 IM or PM phenotypes to the Control group subset with CYP2D6 IM or PM phenotypes using a two-sided two-sample t-test or Mann Whitney test, as appropriate, with a type 1 error of 0.05. The effect of genotype guided opioid therapy on the secondary endpoint clinically significant pain reduction, defined as a 30% decrease, will be assessed by comparing the Intervention group subset with CYP2D6 IM or PM phenotypes the Control group subset with CYP2D6 IM or PM phenotypes using a test of two-proportions with an alpha of 0.05. Participants that have other CYP2D6 phenotypes will not be included in these analyses.

Depression

The effect of genotype guided antidepressants therapy on the secondary endpoint depression remission and achieving 5% reduction in PHQ-8 scores will be assessed by comparing the Intervention group subset with CYP2D6 UM or PM or CYP2C19 UM, RM, or PM phenotypes the

Control group subset with CYP2D6 UM or PM or CYP2C19UM, RM, or PM phenotypes using a test of two-proportions with an alpha of 0.05. The effect of genotype guided antidepressants therapy on the secondary endpoints, medication adherence, PHQ-8 scores, and medication side effect severity burden, will be assessed by comparing the Intervention group subset with CYP2D6 UM or PM or CYP2C19 UM, RM, or PM phenotypes the Control group subset with CYP2D6 UM or PM or CYP2C19 UM, RM, or PM phenotypes using a two-sided Mann Whitney test with an alpha of 0.05. Participants that do not have metabolizer phenotypes will not be included in these analyses.

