Primary Endpoint	
Acute Pain: Silverman Integrated Analgesic Assessment (SIA) score (a composite of pain and opioid usage) at 10 days post-surgery in participants who are genetically or pheno-converted CYP2D6 IM or PM
 
Chronic Pain: Pain control, defined as change in the composite pain intensity score from baseline to 3-months in participants who are genetically or pheno-converted CYP2D6 IM or PM
 
Depression: Depression symptom control, defined as change in PROMIS depression 8A scores from baseline to 3-months in genetically or pheno-converted CYP2D6 UM/PM or CYP2C19 UM/RM/PM

Secondary Endpoints	
Acute Pain:
 
 • Pain intensity at 10 days post-surgery • Opioid usage at 10 days post-surgery • Prescription pain medication misuse score 3 months post-surgery • Mobility score 1-month post-surgery • Opioid persistence 6 months post-surgery 
Chronic Pain:
 
 • Pain reduction magnitude at 3-month follow-up, relative to baseline • Achievement of clinically significant pain reduction (30%) by 3-month follow-up, relative to baseline • Prescription pain medication misuse score at 3-month follow-up 
Depression:
 
 • Change in PHQ-8 scores between baseline and 3 months • Achieve 50% reduction in PHQ-8 scores at 3 months, relative to baseline • Medication side effects severity burden at 3 months • Participant medication adherence at 3 months • Achieve remission at 6 months defined as PROMIS depression score ≤ 16 • Achieve remission at 6 months, defined as PHQ-8 score ≤ 4 
All Trials:
 
 • Overall well-being at 6 months in all randomized participants • Concordance between metabolizer phenotype and prescribed medication • Sub-domains of the PROMIS 43 survey: pain interference, physical function, sleep disturbance, social role and activities functioning, fatigue, anxiety, and depression at 6-month follow-up
Statistical Analyses	
Acute Pain:
 
 • The effect of genotype guided opioid therapy on pain control will be determined by comparing the 10-day post-surgery SIA scores of the Intervention arm participant with CYP2D6 IM or PM phenotypes to the 10-day post-surgery SIA scores of the Control arm participant with CYP2D6 IM or PM phenotypes using a two-sided t-test or a two-sided Mann Whitney

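### Overall well-being at 6 months has an adjusted test in the synopsis and an unadjusted one in section 10.5; one baseline-adjusted model per trial would settle the conflict and gain precision

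*Combined protocol and SAP*

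**What the plan says.** The synopsis lists "Overall well-being at 6 months in all randomized participants" as a secondary endpoint for all three trials. Its statistical analyses entry for all trials compares every Intervention participant with all "Control participants at 6-month follow-up using ANOVA, adjusting for baseline differences in the two groups". It does not say which baseline variables enter the model, and it does not mention the sub-domains.

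Section 10.5 describes an intent-to-treat analysis "comparing the well-being (or sub-domain) T-scores from the 6-month follow-up assessments in the Intervention group compared to the control group". The test is a "two-sided two-sample t-test or Mann Whitney test, as appropriate, stratified by participant population (acute pain, chronic pain, depression"). Its two-sided significance level is 0.05. No baseline value or stratification factor other than trial enters the test. The same sentence covers the seven sub-domains.

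Four other places bear on this:

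- Section 7.3 and Table 8 schedule the PROMIS 43 (adults) or PROMIS pediatrics 37 (ages 8 to 17) at baseline and at 1, 3 and 6 months. The well-being row of Table 8 covers all three trials.
- Section 11.2 defines overall well-being as one T-score from either instrument, centred at 50 with SD 10.
- Section 4.1 stratifies by trial and by site or clinic. It also stratifies Chronic Pain by depression status, and "the randomization for the acute pain and depression trials will be stratified by pediatric/adult".
- Section 10.4 (Depression) says of the primary endpoint: "Pediatric depression T-scores will be transformed to the adult scale using a published crosswalk for a combined analysis". No such rule is given for well-being or its sub-domains.

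**The concern.** The two statements cannot both be the planned analysis of overall well-being: one adjusts for baseline and the other does not, so they can return different p-values from the same data. Section 10.9 makes no multiplicity adjustment for secondary endpoints. It relies on nominal p-values and on having prespecified the outcomes, and that protection is weaker when the test itself is open. Section 10.5 adds a further choice, between a t-test and a Mann-Whitney test, without a rule for making it.

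There is also a loss of precision. The baseline score of the same instrument is already collected and is the obvious covariate, yet the section 10.5 test ignores it.

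A smaller gap concerns Acute Pain and Depression, the two trials that enrol children. All randomised participants are compared on a variable that section 11.2 builds from two different instruments, with no statement of how the scores are brought together.

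**Working it through.** **The two statements side by side.**

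| | Synopsis | Section 10.5 |
|---|---|---|
| Overall well-being | ANOVA, adjusted for unnamed baseline differences | t-test or Mann-Whitney, unadjusted |
| Sub-domains | no test stated | t-test or Mann-Whitney, unadjusted |
| Population | all randomised | intent to treat |

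**Check of the plan's own figures.** The documents give no sample size, power or baseline correlation for well-being. The nearest figures are the primary-endpoint sizes in section 10.1: 152, 134 and 271 per arm for effect sizes 0.375, 0.40 and 0.28 at two-sided alpha 0.049 and 90% power. The exact noncentral t calculation returns 152, 134 and 271, so the plan's framework reproduces.

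**Inputs for well-being.** Completers per arm from Table 9: 845 (Acute Pain), 447 (Chronic Pain), 678 (Depression). Alpha is 0.05 two-sided (section 10.5). SD is 10 (section 11.2); this is the reference SD of the T-score conversion, and the SD in these samples could differ. The baseline-to-6-month correlation r is an assumption, shown from 0.3 to 0.7.

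**Relative gain.** Adjusting for the baseline score multiplies the residual variance by 1 − r², so the equivalent sample-size factor is 1/(1 − r²). Neither depends on n or on the SD.

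| r | variance reduction r² | standard error ratio √(1 − r²) | sample-size factor |
|---|---|---|---|
| 0.3 | 9% | 0.954 | 1.10 |
| 0.5 | 25% | 0.866 | 1.33 |
| 0.7 | 49% | 0.714 | 1.96 |

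At r = 0.5, 845, 447 and 678 per arm act like 845/0.75 = 1127, 447/0.75 = 596 and 678/0.75 = 904.

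**Detectable difference at 90% power.** Unadjusted, this is (1.960 + 1.282) × 10 × √(2/n). Adjusted, it is multiplied by √(1 − r²). Results in T-score points:

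| | Acute Pain | Chronic Pain | Depression |
|---|---|---|---|
| Unadjusted | 1.58 | 2.17 | 1.76 |
| r = 0.3 | 1.50 | 2.07 | 1.68 |
| r = 0.5 | 1.37 | 1.88 | 1.52 |
| r = 0.7 | 1.13 | 1.55 | 1.26 |

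For a true difference of 1.5 points (illustrative), unadjusted power is 86.9%, 61.1% and 78.9%. Adjusted power is 89.8%, 65.2% and 82.5% at r = 0.3, and 94.5%, 73.5% and 89.0% at r = 0.5. These figures concern the t-test; the Mann-Whitney option also leaves the baseline score out.

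**Mixed instruments (Acute Pain and Depression).** If a share p of participants is pediatric and the two instruments differ in mean by g points, ignoring age group multiplies the variance by 1 + p(1 − p)(g/10)². The documents give neither p nor g. With assumed p = 0.10 and g = 5 the factor is 1 + 0.09 × 0.25 = 1.02. With assumed p = 0.20 and g = 10 it is 1 + 0.16 × 1 = 1.16.

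**The case against.** The case for leaving this alone has substance. Well-being is a secondary endpoint with nominal p-values, and the unadjusted test already detects about 1.6 to 2.2 points at 90% power. The synopsis lists covariate-adjusted additional analyses, section 10.6 lists pediatric and adult sub-groups, and section 10.2 defers detail to separate analysis plans for each trial. The size of the gain rests on a correlation that the documents do not give. It may be low in Acute Pain, where the baseline survey precedes surgery and the outcome comes six months after it.

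Most of this limits the size of the point and leaves its existence untouched. The additional covariate analyses do not remove the conflict, because the synopsis names the adjusted ANOVA as the comparison itself and lists the additional analyses separately. A later analysis plan cannot agree with both passages.

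Some stronger readings are tempting but not supported:

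- A reader might take the synopsis to adjust for the baseline well-being score. It names no covariate, and section 10.6 uses similar language for characteristics such as age, sex, income and insurance.
- A reader might see the combining of adult and pediatric scores as peculiar to section 10.5. It is inferred from sections 10.5 and 11.2, the all-participants comparison in the synopsis implies it equally, and it cannot arise in Chronic Pain, where the minimum age is 18.
- A reader might take the section 10.4 crosswalk as a general rule that pediatric scores must be converted before combination. It is stated only for the primary depression T-score, and nothing shows that a crosswalk exists for the well-being composite.

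**Conclusion.** The point holds as a conflict between two current statements about overall well-being, together with an avoidable loss of precision that extends to the sub-domains. For the sub-domains there is no conflict, since only section 10.5 gives a test.

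The direction of the precision loss is certain for any non-zero baseline correlation. Its size is not: 9% to 49% of residual variance, or about 10% to 96% more participants, for an assumed r of 0.3 to 0.7. The upper end should not be quoted alone, and r need not be the same in the three trials.

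The missing rule for PROMIS 43 and PROMIS 37 is a secondary gap, confined to Acute Pain and Depression and shared by both passages. A reader might infer that it biases the arm comparison. Randomisation stratified by pediatric/adult argues against that; what is affected is precision and the meaning of a difference on a mixed scale.

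Primary conclusions are unaffected. The wording should still be corrected before analysis.

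**What to change.** In both the synopsis and section 10.5, name one analysis per trial for overall well-being and for each sub-domain: ANCOVA of the 6-month T-score on arm, baseline T-score and the randomisation strata. The strata are site, with sparse clinics combined under a stated rule; pediatric/adult in Acute Pain and Depression; and depression status in Chronic Pain. Replace the open choice between t-test and Mann-Whitney by a rank-based version of the same analysis, as a sensitivity analysis if residuals are clearly non-normal.

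In Acute Pain and Depression, keep the pediatric/adult term and state one of two rules: link the PROMIS 37 and PROMIS 43 scores, or estimate the arm difference within each age group and combine the two estimates. The age term alone is not enough, because it removes a mean shift but does not put two instruments on one scale.

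All variables are already scheduled for collection, so no new data are needed. The cost is the wording, slightly more modelling, and a rule for small strata: section 4.1 allows stratification by clinic, and the synopsis expects 11 sites with about 60 to 80 clinics.
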